### Grading Criteria

The study site will grade the severity of adverse events experienced by the study subjects according to the criteria set forth in the National Cancer Institute’s Common Terminology Criteria for Adverse Events 4.0, referred to herein as the NCI-CTCAE manual. This document provides a common language to describe levels of severity, to analyze and interpret data, and to articulate the clinical significance of all adverse events. Adverse events will be graded on a scale from 1 to 5 according to the following standards in the NCI-CTCAE manual: Grade 1 = mild adverse event. Grade 2 = moderate adverse event. Grade 3 = severe and undesirable adverse event. Grade 4 = life-threatening or disabling adverse event. Grade 5 = death.

Events grade 3 or higher will be recorded on the appropriate AE case report form for this study, which will be a printable pdf form that can be filled out electronically or printed on paper, such that the form can be scanned or uploaded into electronic data system(s). For grading an abnormal value or result of a clinical or laboratory evaluation (including, but not limited to, a radiograph, ultrasound, electrocardiogram, etc.), a treatment-emergent adverse event is defined as an increase in grade from baseline or from the last post-baseline value that doesn’t meet grading criteria. Changes in grade from screening to baseline will also be recorded as adverse events, but are not treatment-emergent. If a specific event or result from a given clinical or laboratory evaluation is not included in the

NCI-CTCAE manual, then an abnormal result would be considered an adverse event if changes in therapy or monitoring are implemented as a result of the event/result.

### Attribution Definitions

The relationship, or attribution, of an adverse event to the study therapy regimen or study procedure(s) will initially be determined by the site investigator and recorded on the appropriate AE pdf /printed case report form. Final determination of attribution for safety reporting will be determined by DSMB. The relationship of an adverse event to study procedures will be determined using the descriptors and definitions provided in Table 1. For additional information and a printable version of the NCI-CTCAE manual, consult the NCI-CTCAE web site: <http://ctep.cancer.gov/reporting/ctc.html>.

**Table 1. Attribution of Adverse Events**

Code	Descriptor	Relationship (to primary investigational product and/or other concurrent mandated study therapy or study procedure)
UNRELATED CATEGORY		
1	Unrelated	The adverse event is clearly not related: there is insufficient evidence to suggest a causal relationship.
RELATED CATEGORIES		
2	Possible	The adverse event has a reasonable possibility to be related; there is evidence to suggest a causal relationship.
3	Definite	The adverse event is clearly related.

### Collection and Recording of Adverse Events

#### Collection Period

Adverse events will be collected from delivery until hospital discharge.

#### Collecting Adverse Events

Adverse events (including SAEs) may be discovered through any of these methods:

- Interviewing the subject or parent
- Receiving an unsolicited complaint from the subject or parent.
- In addition, an abnormal value or result from a clinical or laboratory evaluation can also indicate an adverse event, as defined in Section 2, *Definitions, Grading and Attribution of Adverse Events*.

#### Recording Adverse Events

Throughout the study, the investigator will record adverse events and serious adverse events as described previously (Section 2.1, *Definitions*) on the uploadable pdf or printed AE/SAE CRF) regardless of the relationship to study procedure. Once recorded, an

AE/SAE will be followed until it resolves with or without sequelae, or until the end of study participation, or until 30 days after the subject prematurely withdraws (without withdrawing consent)/or is withdrawn from the study, whichever occurs first.

### **Reporting of Serious Adverse Events and Adverse Events**

This section describes the responsibilities of the site investigator to report serious adverse events to the sponsor via the electronic safety system. Timely reporting of adverse events is required by 21 CFR and ICH E6 guidelines.

#### **Reporting of Serious Adverse Events to OSCTI**

Site investigators will report all serious adverse events (see Section 2.1, *Serious Adverse Event*), regardless of relationship or expectedness within 24 hours of discovering the event. For serious adverse events, all requested information on the AE/SAE uploadable CRF will be provided. However, unavailable details of the event will not delay submission of the known information. As additional details become available, the AE/SAE uploadable CRF will be updated and submitted.

#### **Reporting to Health Authority**

After an adverse event requiring 24 hour reporting (per Section 4.1, *Reporting of Serious Adverse Events to Sponsor*) is submitted by the site investigator and assessed by OSCTI there are two options for OSCTI to report the adverse event to the appropriate health authorities:

##### Annual Reporting

OSCTI will include in the annual study report to health authorities all adverse events classified as:

- Serious, expected, suspected adverse reactions (see Section 2.1, *Suspected Adverse Reaction* and *Unexpected Adverse Event*).
- Serious and not a suspected adverse reaction (see Section 2.1, *Suspected Adverse Reaction*).

Safety data will be made public in a timely manner on clinicaltrials.gov and through publications.

##### Expedited Safety Reporting

This option applies if the adverse event is classified as one of the following:

**Category 1: Serious and unexpected suspected adverse reaction [SUSAR]** The sponsor shall report any suspected adverse reaction that is both serious and unexpected (see Section 2.1, *Suspected Adverse Reaction* and *Unexpected Adverse Event* and 21 CFR 312.32(c)(1)i). The sponsor shall report an adverse event as a suspected adverse reaction only if there is evidence to suggest a causal relationship between the study drug and the adverse event, such as:

1. A single occurrence of an event that is uncommon and known to be strongly associated with procedure exposure (e.g., burns);
2. One or more occurrences of an event that is not commonly associated with drug exposure, but is otherwise uncommon in the population exposed to the procedure.

3. An aggregate analysis of specific events observed in a clinical trial (such as known consequences of the underlying disease or condition under investigation or other events that commonly occur in the study population independent of the intervention) that indicates those events occur more frequently in the treatment group than in a concurrent or historical control group.

#### **Category 2: Any findings from studies that suggests a significant human risk**

The sponsor shall report any findings from other epidemiological studies, analyses of adverse events within the current study or pooled analysis across clinical studies or animal or *in vitro* testing (e.g. mutagenicity, teratogenicity, carcinogenicity) that suggest a significant risk in humans exposed to the intervention that would result in a safety-related change in the protocol, informed consent, investigator brochure or package insert or other aspects of the overall conduct of the study.

OSCTI shall notify the appropriate health authorities and all participating investigators of safety reporting within 15 calendar days; unexpected fatal or immediately life-threatening suspected adverse reaction(s) shall be reported as soon as possible or within 7 calendar days.

#### **Reporting of Adverse Events to IRB**

All investigators shall report adverse events, including expedited reports, in a timely fashion to the IRB in accordance with applicable regulations and guidelines. All Safety Reports shall be distributed by OSCTI or designee for IRB submission.

#### **Reporting of Other Safety Information**

An investigator shall promptly notify the site IRB as well as the OSCTI Safety Officer when an “unanticipated problem involving risks to subjects or others” is identified, which is not otherwise reportable as an adverse event.

#### **Review of Safety Information**

#### **Medical Monitor Review**

The OSCTI and DSMB shall compile new and accumulating information on AEs, and SAEs recorded by the study site(s) on appropriate, uploadable CRFs. In addition, DSMB shall review and make decisions on the disposition of the SAE reports received (See Section 4.1, *Reporting of Serious Adverse Events to Sponsor*).

## **DSMB Review**

The PIs will establish an independent DSMB to review and interpret data generated from the study and to review the protocol prior to their implementation. Its primary objectives are to ensure the safety of study subjects, the integrity of the research data and to provide the PIs with advice on the ethical and safe progression of the study. The DSMB advises on research design issues, data quality and analysis, and research participant protections.

The DSMB members will be invited by the PIs and will include three experts in the following fields: biostatistics, neonatology and obstetrics. The DSMB will schedule regular committee meetings, recording all meeting minutes and summarizing the committee recommendations for the PIs.

The DSMB will have semiannual teleconferences to review the protocol with respect to ethical and safety standards, monitor the safety of the ongoing trial, the integrity of the data with respect to original study design, and provide advice on study conduct. The DSMB will periodically monitor data quality, including accrual, retention, data submission timeliness, data completeness, protocol adherence and adverse events. The DSMB may recommend protocol modifications based on concern for subject welfare and scientific integrity.

### Planned DSMB Reviews

The Data and Safety Monitoring Board (DSMB) shall review safety data semiannually during planned DSMB Data Review Meetings. Data for the planned safety reviews will include, at a minimum, a listing of all reported AEs and SAEs. The DSMB will be informed of an Expedited Safety Report within 24 hours by uploading the report to a secure site and informing DSMB members by email that there is a message for them.

### Ad hoc DSMB Reviews

In addition to the pre-scheduled data reviews and planned safety monitoring, the DSMB may be called upon for *ad hoc* reviews. The DSMB will review any event that potentially affects safety at their own initiative or at the request of the PIs or OSCTI. In addition, the following events will trigger an *ad hoc* comprehensive DSMB Safety Review:

- Any death that occurs in the study, which is possibly or definitely related to study intervention.
- The occurrence of a Grade 3 or higher unexpected SAE in 3 or more of the study participants who have received the study intervention.

After review of the data, the DSMB will make recommendations regarding study conduct and/or continuation.

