**G. Gender/Minority/Pediatric Inclusion for Research**

Since this study aims to optimize outcomes for newborn preterm neonates with an intervention that is performed at the time of delivery such a study cannot be completed without participation of neonates or their mothers. As mentioned, the risks to mothers

should not be increased because of this intervention as there are no additional interventions beyond standard of care delayed cord clamping that will be required of mothers. On the neonatal side, there is a risk for neonatal iatrogenic hyperthermia defined as temperature  $>37.5$  degrees Celsius; however, no clinically important adverse outcomes have been identified in previous studies.

This study involves viable neonates (gestational age  $\geq 32$  weeks) and pregnant women. The proposed interventions are aimed at neonatal resuscitation, as such they should not impact maternal wellbeing. The intervention will be completed in a sterile fashion similar to all the procedures of the cesarean delivery. The research is aimed at directly improving neonatal outcomes, and this particular intervention has been demonstrated to be safe if applied at a different time point in the neonatal resuscitation process. The informed consent process will include the risks and potential benefits associated with the proposed study. As expected, assent cannot be obtained from neonates. When obtaining consent from mothers younger than 18 years old, we will obtain consent from the patient and her parents, as she will be making decisions regarding her child's wellbeing immediately after birth and is considered empowered to do so under Oklahoma law. The overall risk level for pregnant patients is low as the procedures do not affect their wellbeing. The risk for neonates is also low because similar interventions have been investigated in the past at a different time point in the neonatal resuscitation process without evidence of significant adverse consequences.

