### Unexpected Adverse Event

An adverse event or suspected adverse reaction may be related to the study agent, or study procedures, or may be unrelated. Procedure-related adverse events or suspected adverse events are considered “unexpected” if not listed in the relevant *package insert* or not listed at the specificity, severity or rate of occurrence that has been observed.

“Unexpected” also refers to adverse events or suspected adverse reactions that are mentioned in the package insert as occurring with a class of drugs or as anticipated from the pharmacological properties of the drug, but are not specifically mentioned as occurring with the particular drug under investigation (21 CFR 312.32(a)).

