### Temporary Suspension of enrollment for ad hoc DSMB Safety Review

[Please also see below Stopping Rules and Withdrawal Criteria]

In the event of a death or occurrence of Grade 3 or higher related and unexpected SAE in 3 or more study participants, there will be a temporary halt in enrollment.

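### Apart from deaths, the automatic DSMB review and the enrollment halt count only unexpected serious events, and the plan does not settle whether device burns qualify

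*Combined protocol and SAP*

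**What the plan says.** Two sections of the combined protocol and SAP set automatic safety actions, and each has a death limb and an event-count limb.

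- *Ad hoc DSMB Reviews* forces a comprehensive review for "Any death that occurs in the study, which is possibly or definitely related to study intervention", or for "The occurrence of a Grade 3 or higher unexpected SAE in 3 or more of the study participants" who received the intervention.
- *Temporary Suspension of enrollment for ad hoc DSMB Safety Review* pauses enrollment: "In the event of a death or occurrence of Grade 3 or higher related and unexpected SAE in 3 or more study participants".

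Under *Unexpected Adverse Event*, an event is unexpected if the package insert does not list it, or if it is "not listed at the specificity, severity or rate of occurrence that has been observed". The test is the insert, not the protocol's own account of risk.

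*Expedited Safety Reporting*, under its category for serious and unexpected suspected reactions, illustrates causal evidence with a single uncommon event "known to be strongly associated with procedure exposure (e.g., burns"). Section G says of the infant that "there is a risk for neonatal iatrogenic hyperthermia".

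**The concern.** Expectedness is a regulatory-reporting idea: it decides which serious reactions go to authorities quickly and which wait for the annual report. Used as a condition for a safety pause, it can make the pause less likely to apply the better documented a harm is. Here infants are delivered directly onto an activated thermal mattress, so a burn is a harm the investigators can foresee, and *Interim Analysis of Safety Data* lists skin burns by name. If the insert lists burns, related serious burns may drop out of the event count in both rules. If it does not, they count. A DSMB member reading the protocol cannot tell which applies, so the automatic rules are undefined for the device harm they would most obviously be expected to cover.

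**Working it through.** The plan states no operating characteristic for these rules, so there is no figure to reproduce. The check is a comparison of the texts, then a calculation of whether the interim test could stand in for a count.

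**1. Filters on each limb**

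| Rule | Death limb | Event-count limb (3 or more participants) |
|---|---|---|
| Ad hoc review | possibly or definitely related; no expectedness condition | Grade 3+, SAE, unexpected; treated participants |
| Enrollment halt | any death; no expectedness condition | Grade 3+, SAE, unexpected, related; study participants |

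Expectedness therefore filters only the non-fatal count, but it does so in both rules.

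**2. Status of a burn.** The definition refers to the insert, which is not in the documents. *Expedited Safety Reporting* places burns under serious and unexpected reactions but does not say whether the insert lists them. The status is unsettled.

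**3. Size of the case.** 74 participants at 1:1 gives 74/2 = 37 in the intervention arm. Three burns is 3/37 = 8.1%. Suppose each is Grade 3+, meets the SAE definition and is judged related, and the insert lists serious burns at that severity and rate (assumed). Neither count limb is then met.

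**4. Could the interim test fill the gap?** Burns are compared between groups after each third of participants with a Lan-DeMets spending function. No alpha, function shape, boundary or resulting action is stated.

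- First look: 74/3 = 24.7 participants, about 12 per arm. Accrual is 74/(250 × 0.33) years = 10.8 months, so this falls at about 3.6 months.
- Two-sided Fisher p for k burns against 0 with n per arm is 2 × C(n,k)/C(2n,k).
- 3 v 0, n = 12: 2 × 220/2,024 = 0.22.
- 3 v 0, n = 37: 2 × 7,770/64,824 = 0.24.
- Assuming a Pocock-type function at two-sided 0.05, alpha spent at one third is 0.05 × ln(1 + (e − 1)/3) = 0.023. With n = 12, 5 v 0 gives 2 × 792/42,504 = 0.037 (not crossed) and 6 v 0 gives 2 × 924/134,596 = 0.014 (crossed). An O'Brien-Fleming-type function would need more.

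Three serious burns against none would not cross such a boundary at the first look or at full enrollment.

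**5. How often would a wider count fire?** The exact binomial P(3 or more of 37) is 0.006, 0.04 and 0.28 at assumed burn rates of 1%, 2% and 5%; the documents give no rate. These count all burns, so they are upper limits for Grade 3+ SAEs. For any hyperthermia, the rates cited in section I give 0.48 at 7% and 0.999 at 28%, so a count of three without a severity filter would have about an even chance of firing at the lower rate and would be near certain at the higher one.

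**The case against.** The strongest reply is that serious burns would be seen promptly anyway. *Reporting of Serious Adverse Events to OSCTI* requires every SAE within 24 hours whatever its relationship or expectedness. *Medical Monitor Review* obliges the DSMB to decide the disposition of those reports. *Ad hoc DSMB Reviews* lets the DSMB, the PIs or the sponsor start a review of any safety event. Expedited Category 2 findings have no expectedness condition, and the DSMB hears of expedited reports within 24 hours. *Study Stopping Rules* allows termination for unexpected rates of severe or serious events. All of this stands, and it means the plan does not leave burns to the semiannual meetings alone. None of these provisions, however, ties a number of events to a comprehensive review or a halt.

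A reader might infer four stronger things that the documents do not support.

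- *Both rules respond only to unexpected events.* They do not: the death limbs carry no such condition.
- *No number of burns could trigger action.* The definition keeps a listed event unexpected if its severity or rate is not the one listed. Ten burns in 37 (27%) would be expected only if the insert listed them at about that rate, or if an insert giving no rate were read as covering any rate.
- *Harms the protocol anticipates are thereby expected.* The test is the insert, and the only text that places burns puts them with unexpected reactions.
- *Overheating falls through the same gap.* A temperature just above 37.5 °C would rarely be Grade 3+ or meet the SAE definition, so those filters would usually exclude it before expectedness mattered.

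**Conclusion.** The concern holds in a limited form. What is missing is an automatic comprehensive review or halt for repeated, related, non-fatal serious events that the insert lists; review as such is not missing. The working case is three serious burns in about 37 infants (8.1%), and the planned interim comparison would not substitute for a count (p of 0.22 to 0.24). This rests on an assumption about the insert's content that the documents can neither confirm nor refute, and on the burns meeting the Grade 3+ and SAE criteria. If the insert does not list serious burns at that severity and rate, the present rules already count them and only the ambiguity remains. The point concerns participant safety and clarity of monitoring and does not bear on the efficacy analysis. It should be corrected before enrollment.

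**What to change.** In *Ad hoc DSMB Reviews*, add to the count Grade 3 or higher SAEs judged possibly or definitely related to the wrap or mattress, regardless of expectedness. Keep the existing limb for unexpected SAEs, which does not require relatedness. In *Temporary Suspension of enrollment for ad hoc DSMB Safety Review*, remove the expectedness condition for such related events. Keep the Grade 3+ and SAE filters in both, so that mild hyperthermia does not count. Retain *unexpected* in *Expedited Safety Reporting*, where it serves regulatory reporting. Reconcile that section, *Unexpected Adverse Event* and the two rules so that the status of burns is stated once.

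The cost is two amended sentences and a clarification. The operational downside is possibly an extra DSMB call and a short enrollment pause. At assumed burn rates of 1% to 2%, the chance of three or more in the intervention arm is at most 0.04.

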### Temporary Suspension of enrollment for ad hoc DSMB Safety Review

[Please also see below Stopping Rules and Withdrawal Criteria]

In the event of a death or occurrence of Grade 3 or higher related and unexpected SAE in 3 or more study participants, there will be a temporary halt in enrollment.

## **Interim Analyses**

### **Interim Analysis of Efficacy Data**

A formal interim efficacy analysis is not planned. Given the timing of recruitment, duration of follow-up, and targeted sample size, interim efficacy findings would not likely impact the conduct of the trial.

### **Interim Analysis of Safety Data**

Safety data will be collected throughout the trial. A DSMB will be formed and will review the blinded data at semi-annual intervals. Formal interim statistical analysis will be performed after every third of the participants have completed the trial using the Lan DeMets (at) spending function for between-group comparisons.

The following events will be formally monitored among the maternal/infant dyads:

- Wound infections
- Skin burns
- Hyperthermia at arrival to the warmer - Temperature > 37.5 degrees Celsius
- Length of NICU admission
- Sepsis
- Intraventricular hemorrhage
- Death

Each of these events will be monitored separately.

### **Futility Analysis**

No futility analysis will be performed, due to the pilot nature of this trial.

### **Study Stopping Rules**

The study may be prematurely terminated for the following reasons:

1. Unexpected rates of severe or serious adverse events
2. Any other reason deemed appropriate by the DSMB

